4.3.1 Dose escalation rules

Dose escalation to a higher dose will be driven by an evaluation by the DSMB. At the time of DSMB evaluation, the last patient in the current dose level cohort must have received the 2nd dose and must have accumulated safety data for 8 weeks following the first dose. This allows for the DLT evaluation period to include an assessment of a potential delay in dose 2 due to toxicity concerns, as described for DLT number 5 in Section 4.3.2.

If one of the 3 patients in a dosing cohort experiences a DLT, 3 additional patients are added to the same dose level cohort. If 2 or more patients among these 6 patients experience DLTs, no further dose escalation can occur, and lower dose levels can be further explored. Dose escalation will continue until not more than 1 out of 6 patients experience DLT in a dose level cohort or the highest dose level group has completed treatment or no trial stopping criterion has been met. See Figure 2.

[figure not shown]

Figure 2: Dose-escalation according to a 3+3 design

Dose escalation will continue until not more than 1 out of 6 patients experiences a DLT in a dose level cohort (see DLT definitions in Section 4.3.2) or the dose level of

Clinical Study: ES2B-C001-S01 EU CT No.: 2024-516333-12-00

treatment has been completed (maximum administered dose MAD) or a trial stopping criterion has been met. The stopping criteria for dose escalation and trial are provided in Section 7.

Patients experiencing DLT will have their administration of adjuvanted or non-adjuvanted ES2B-C001 discontinued. These patients are allowed to remain in the trial to follow safety, disease progression and immune response. The DSMB will convene and recommend whether a re-start of these patients' treatment is advised and if a dose reduction may be required.

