	 Total anti-HER2 Immunoglobulin titers in sera by enzyme-linked immunosorbent assay (ELISA). Isotyping of anti-HER2 Immunoglobulins in sera (e.g. IgM, IgG (IgG1-4), IgD, IgE, IgA). Exploratory Endpoints: Percentage of patients with measurable disease at baseline achieving Complete Remission (CR) or Partial Response (PR) according to RECIST 1.1 as assessed by the investigator during routine follow up. Percentage of patients with Disease Control Rate (DCR) according to RECIST 1.1 as assessed by the investigator during routine follow up. Progression free survival (PFS) in patients with Stable Disease (SD), or PR, at the time of first dosing of ES2B-C001 alone or in combination with the adjuvant according to RECIST 1.1. Disease-free survival (DFS) in patients with CR at the time of first dosing of ES2B-C001 alone or in combination with the adjuvant according to RECIST 1.1. Overall survival (OS). This dose escalation part will be conducted according to an adapted 3+3
Study Period	 design. For each patient enrolled, there will be a: Screening period between 1 and 28 days prior to the first dose ES2B-C001. An out-patient treatment period of 12 weeks; Safety follow-up for ~6 weeks following the last dose of ES2B-C001. An end-of-study visit.
Study Design	The trial is a first-in-human, phase I, open-label, dose-escalating trial to assess the safety and tolerability of ES2B-C001 combined with [adjuvant] or without [adjuvant], in patients with human epidermal growth factor receptor 2 (HER2) expressing metastatic breast cancer.

Clinical Study: ES2B-C001-S01 EU CT No.: 2024-516333-12-00

Clinical Study: ES2B-C001-S01 EU CT No.: 2024-516333-12-00

The decision to escalate the dose to the next dosing cohort or initiate the expansion part will be taken by the sponsor based on the data safety monitoring board (DSMB) recommendations. The DSMB will base their recommendations on an evaluation of accumulated safety data and, if available, on immunogenicity data (antibody titers), whenever 3 patients of a specific cohort have received at least one dose, and the last patient completed the DLT observation period of 8 weeks.

Enrollment will be fully staggered in each of the populations, meaning that an observation period of 3 weeks plus 24 hours is foreseen before the second patient is dosed in one cohort. Dosing of the next subject in each cohort should ideally not take place until 1 week after the preceding patient has received the first dose.

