9.2 Analysis Sets

Safety Set: will include all patients who received at least 1 dose of the trial drug. All safety/tolerability and DLT analyses will be performed using this analysis set and will be descriptive, with no statistical inference to be drawn from the data.

Immunogenicity Set: will include all patients who received at least 1 dose of the trial drug and have provided immunogenicity data. All immunogenicity analyses will be performed using this population.

Efficacy-evaluable Set: will include all patients receiving at least 1 dose of the trial drug and who have provided at least 1 tumor evaluation at baseline and 1 tumor evaluation following treatment administration.

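### The synopsis and Section 4.3.1 set different triggers for the DSMB escalation review, and the DLT rate in 9.2 and 9.3.1 uses a wider group than the replacement rule implies

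*Protocol*

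**What the plan says.** The protocol states the trigger twice. In the synopsis (1.1, Study Design) the DSMB makes its recommendation "whenever 3 patients of a specific cohort have received at least one dose, and the last patient completed the DLT observation period of 8 weeks". In 4.3.1 the condition for that review is that "the last patient in the current dose level cohort must have received the 2nd dose"; the same patient also needs 8 weeks of data counted from dose 1. Section 4.3.1 gives its reason: "This allows for the DLT evaluation period to include an assessment of a potential delay in dose 2 due to toxicity concerns". It refers there to DLT number 5 in 4.3.2, a treatment delay of more than 14 days because of a related adverse event.

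Two further sentences in 4.3.1 bear on whether dose 2 will be given after a DLT. The first is "Patients experiencing DLT will have their administration of adjuvanted or non-adjuvanted ES2B-C001 discontinued". A later one in the same paragraph leaves a way back: "The DSMB will convene and recommend whether a re-start of these patients' treatment is advised and if a dose reduction may be required".

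Sections 4.3 and 7.1 let the sponsor replace, at its discretion, patients who stop for reasons other than toxicity before they have DLT-evaluable data. The text at hand does not define that term. Section 9.2 defines the Safety Set as all patients with at least one dose and adds: "All safety/tolerability and DLT analyses will be performed using this analysis set". Section 9.3.1 applies a cut-off of at least 33% of patients with a DLT on that set.

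**The concern.** In a first-in-human 3+3 trial, this trigger decides when a dose level is cleared and on how much exposure. Two versions in the same protocol allow the same cohort to be ready for review under one section and not under the other.

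The version in 4.3.1 also has a gap. It makes receipt of dose 2 a condition but does not say what follows if the last patient stops before it. A related delay of more than 14 days is itself a DLT, and a DLT leads to discontinuation. The event that the dose-2 condition is meant to make visible can therefore keep the condition from being met.

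Finally, the replacement rule presupposes a DLT-evaluable group, while the analysis sections count everyone dosed. The escalation count and the reported DLT rate can then point in different directions for the same dose level.

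**Working it through.** **1. The two triggers side by side.**

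| Last patient of the cohort | Synopsis | 4.3.1 |
|---|---|---|
| Two doses, 8 weeks of data | met | met |
| One dose, 8 weeks of data | met | not met |

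The second row is the contradiction. It needs no arithmetic.

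**2. When the gap in 4.3.1 affects escalation.** Take the 3+3 rule in 4.3.1: 0/3 escalate, 1/3 add three patients, two or more no escalation, and at most 1/6 allows escalation.
- First three patients: in 4 of the 8 possible sequences the third patient has a DLT. One gives expansion and three give no escalation. None gives escalation.
- After expansion for 1/3: there are 3 × 8 = 24 sequences. In 12 of them the sixth patient has a DLT. That makes at least 2/6, so none gives escalation.

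In the plain 3+3, then, a DLT in the last patient never leads to an escalation that the dose-2 condition could block. Two cases remain:
- The last patient stops before dose 2 for a non-toxicity reason, is followed for 8 weeks and is not replaced. With 0/3, or 1/6 after expansion, the count allows escalation and the synopsis trigger is met, but 4.3.1 is not.
- A cohort is electively expanded, escalation is decided on all six, and 0/5 is followed by a DLT in patient 6. The count 1/6 allows escalation. The probability is p(1−p)^5:

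| True DLT rate p (illustrative) | p(1−p)^5 |
|---|---|
| 5% | 3.9% |
| 10% | 5.9% |
| 20% | 6.6% |
| 33% | 4.5% |

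These are upper bounds, because they include DLTs that occur after dose 2.

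**3. Is dose 2 needed to judge DLT number 5?** The dosing schedule is not visible. Section 8.3.5.2 places the 5th dose at week 12, so I assume four equal intervals of 12/4 = 3 weeks and also try 2 and 4 weeks. Day 1 is the first dose, and the DLT window ends on day 1 + 56 = 57.

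| Interval | Dose 2 due | Delay exceeds 14 days |
|---|---|---|
| 2 weeks | day 15 | day 30 |
| 3 weeks | day 22 | day 37 |
| 4 weeks | day 29 | day 44 |

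In each case the delay can be judged before day 57 even if dose 2 is never given.

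**4. Earlier patients.** By the staggering in 4.3, patient 2 follows patient 1 by at least 3 weeks plus 24 hours, and patient 3 follows at least 1 week later. When patient 3 reaches 8 weeks, patient 2 is at 8 + 1 = 9 weeks or more and patient 1 at 8 + 1 + 3 = 12 weeks or more. They have had the time. If one of them stopped after one dose, however, neither trigger excludes that patient.

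**5. The denominator.** Two DLTs among six evaluable patients: 2/6 = 33.3%, which meets the 33% cut-off in 9.3.1. If one further patient was dosed, was not evaluable and was replaced, that patient stays in the Safety Set: 2/7 = 28.6%, which does not. The count rule in 4.3.1 (two or more of six) stops escalation in both cases, so the two sections would disagree about the same level.

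**The case against.** The strongest reply is that little is actually blocked. This largely stands.

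A reader might infer that 4.3.1 can never be satisfied once the last patient has a DLT after dose 1. The documents do not support that: the same paragraph lets the DSMB recommend a re-start, so dose 2 remains possible. A reader might also infer that the DSMB is kept from looking at the very patient who had the DLT. That does not hold either. Sections 4.3 and 10.7 send any potential DLT to the DSMB, 4.3.1 itself adds three patients after 1/3, and 7.5 halts enrollment at two or more of six. Where the gap does block escalation, the effect is delay, not unsafe clearance.

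A third tempting reading puts a size on the weakened clearance. At a true DLT rate of 33%, the chance of seeing no DLT is 0.67^3 = 30% with three patients, 0.67^2 = 45% with two and 67% with one. The last two figures are worst-case bounds only. They treat a one-dose patient as carrying no DLT information, although the window in 4.3.2 runs from the first dose and 7.1 keeps patients who stop treatment in follow-up where possible.

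It can also be said that the DSMB charter, which is not at hand, may define evaluability, and that the Safety Set is a descriptive reporting set. The charter may fill the gap on evaluability, but it should not have to choose between two protocol rules. The reporting set matters because 9.3.1 ties the cut-off for the maximum tolerated dose to it.

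**Conclusion.** The point holds in this form. The two triggers are incompatible in current text, and a last patient with one dose and 8 weeks of follow-up separates them. Read literally, 4.3.1 is unmet when the last patient stops before dose 2 without a re-start or a replacement. That blocks escalation after a non-toxicity stop, and after an elective expansion with 0/5 and then a DLT in patient 6 (at most about 4% to 7% at true DLT rates of 5% to 33%). It does not block an escalation that the plain 3+3 would otherwise allow after a last-patient DLT.

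The dose-2 condition does not reach earlier patients. The denominator in 9.2 and 9.3.1 can move a level with two DLTs from 33.3% to 28.6%, across the cut-off, with a single replaced patient.

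The contradiction and the denominator arithmetic need no assumption beyond one replacement. The timing check rests on an assumed 2- to 4-week dose interval. The point should be settled before the first escalation decision.

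**What to change.** - Reconcile the synopsis and 4.3.1 to one trigger. Which exposure it requires is for the sponsor to choose; this review does not propose one.
- Apply it to every patient of the cohort, not only the last.
- Define DLT-evaluable in the protocol: a patient with a DLT counts regardless of doses received, and a patient without a DLT who falls short of the chosen exposure or observation does not count toward clearing the level.
- Use that group as the denominator for the DLT rate and the 33% cut-off in 9.2 and 9.3.1. Keep the Safety Set for the other safety summaries.

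The cost is protocol wording and an occasional replacement patient. Replacement is already permitted in 4.3 and 7.1, but in practice it would become necessary whenever a cohort is short of evaluable patients. Each replacement can delay a cohort by about 8 weeks or more, in a study planned for 15 months.

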9.1 Sample Size Determination

This is a phase I study following a traditional 3+3 design, and no formal statistical hypothesis will be tested. The sample size was estimated to be 9 evaluable patients assuming 3 possible dose levels. However, due to the cohort expansion design, a maximum of 27 evaluable patients in total could be dosed.

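### Section 4.3.1 contradicts itself on what ends dose escalation: read literally, at most 1 DLT in 6 patients ends it, and so do 2 or more

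*Protocol*

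**What the plan says.** Section 4.3.1 gives the escalation rule in running text around Figure 2.

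- Expansion: "If one of the 3 patients in a dosing cohort experiences a DLT, 3 additional patients are added to the same dose level cohort".
- Limiting result: "If 2 or more patients among these 6 patients experience DLTs, no further dose escalation can occur".
- Next sentence, before Figure 2: "Dose escalation will continue until not more than 1 out of 6 patients experience DLT in a dose level cohort". It then lists two further end conditions: "or the highest dose level group has completed treatment or no trial stopping criterion has been met".
- After Figure 2 the rule is restated: "Dose escalation will continue until not more than 1 out of 6 patients experiences a DLT in a dose level cohort". The last end condition is now "or a trial stopping criterion has been met".

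Other sections bear on the same rule. Section 7.5 temporarily halts enrollment when 2 or more of 6 patients in a dosing group have DLTs, and closes that level if the DLTs are confirmed. Section 4.2 expects progression through the dose levels and equates the MTD with the maximum administered dose if the highest level is reached without unacceptable side effects or DLTs. Section 9.1 states: "This is a phase I study following a traditional 3+3 design". Section 9.1.1 bases the operating characteristics on the pathways of the standard 3+3. The synopsis and Section 4.1 call the design an adapted 3+3.

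**The concern.** A condition placed after the word *until* is the condition at which the activity ends. Both statements put a tolerable result there, at most 1 DLT in 6. A level that passes would therefore end escalation, which is the reverse of what the preceding sentence and Sections 4.2, 7.5 and 9.1.1 imply. The inversion stands on both sides of Figure 2, so it cannot be set aside as a single slip. No other sentence in the visible text of Section 4.3.1 says that escalation may proceed after 0 of 3 or after 1 of 6.

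The closing clauses conflict as well. One ends escalation when no stopping criterion has been met, which literally describes a trial in which nothing has gone wrong. The other ends it when a criterion has been met.

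This rule generates the DLT data from which the MTD, part of the primary objective, is determined. After 1 DLT in 3 patients and then 0 in 3, the text supports two opposite decisions. If the literal one is followed, escalation stops at a level that the rest of the protocol treats as passable.

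**Working it through.** **The plan's own figures.** Section 9.1 gives 9 evaluable patients for 3 dose levels and a maximum of 27. With 3 patients per level, 3 × 3 = 9. With the expansion to 9 per level allowed in Section 4.1, 3 × 9 = 27. Both reproduce, and neither depends on the disputed wording. The values of Table 14 are not shown, so the operating characteristics cannot be reproduced and every DLT rate below is an assumption.

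**The rules side by side, for six patients at one level.**

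| DLTs in 6 | *Until* statements, read literally | Preceding sentence and Section 7.5 |
|---|---|---|
| 0 or 1 | escalation ends | limit not reached |
| 2 or more | end condition not met | no further escalation; enrollment halted |

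Each row contains one rule that ends escalation. Applied together, they leave no six-patient result that permits it.

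**How often the disputed result arises.** The path is 1 DLT in the first 3 patients and 0 in the 3 added. For a true DLT rate p at that level:

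P(1 of 3) × P(0 of 3) = 3p(1 − p)^2 × (1 − p)^3 = 3p(1 − p)^5

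| Assumed p | 3p(1 − p)^5 | Result |
|---|---|---|
| 0.05 | 0.15 × 0.95^5 | 11.6% |
| 0.10 | 0.30 × 0.90^5 | 17.7% |
| 0.20 | 0.60 × 0.80^5 | 19.7% |
| 0.30 | 0.90 × 0.70^5 | 15.1% |
| 0.40 | 1.20 × 0.60^5 | 9.3% |
| 0.50 | 1.50 × 0.50^5 | 4.7% |

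The maximum is 20.1%, at p = 1/6.

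**What the literal reading would do to escalation.** Under the standard 3+3, P(escalate past a level) = (1 − p)^3 + 3p(1 − p)^5. If the *until* clause applies only to six-patient cohorts, the second term is lost and (1 − p)^3 remains. At p = 0.10 this is 0.906 against 0.729; at p = 0.20, 0.709 against 0.512.

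The chance of reaching level 3 is the product over levels 1 and 2:

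- Assumed rates 0.05/0.10/0.20: 0.882 (standard) against 0.625, a difference of 0.257.
- Assumed rates 0.10/0.20/0.30: 0.642 against 0.373, a difference of 0.269.
- Assumed rates 0.30/0.40/0.50: 0.153 against 0.074, a difference of 0.079.

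If the clause is also taken to cover 0 of 3, escalation never leaves level 1 under any rates, because 2 or more DLTs end it too.

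**The case against.** The strongest reply is that the intent can be recovered. The sentence on 2 or more DLTs, Section 7.5, and the Section 4.2 route to the maximum administered dose all point to a conventional 3+3. Escalation is driven by DSMB evaluation and decided by the sponsor, not applied mechanically, and the charter is to hold additional instructions. Figure 2 is not visible here and may show the 1-of-6 branch plainly. The statement before Figure 2 also follows a remark about exploring lower doses, so it may have been meant to say when dose finding ends.

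Much of this stands as evidence of intent and lowers the chance that the literal text would be followed. It does not repair the text. A correct figure or charter would still disagree with the prose. The dose-finding reading requires a different word from escalation and leaves the conflict between the two stopping-criterion clauses untouched. Calling the design adapted does not help either, since no stated adaptation makes a tolerated level the end point.

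A reader might infer two stronger things. One is that the wording licenses escalation above a level with 2 or more DLTs. It does not: the preceding sentence forbids it, and Section 7.5 halts enrollment at that result. The other is that the path to the MTD is blocked outright. That follows only if the clause also covers 0 of 3; if it concerns six-patient cohorts, only the route through 1 of 6 is lost.

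**Conclusion.** Wrong as written: an internal contradiction in an operative rule, not a design choice. It covers the six-patient outcome with at most 1 DLT and the polarity of the stopping-criterion clause. The practical exposure is an early stop after 1 of 3 and then 0 of 3.

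Across assumed true DLT rates of 5% to 50%, each level reached has a 4.7% to 20.1% chance of producing that result. These figures assume independent patients with a common rate at the level. They measure how often the contradiction would have to be resolved in practice, not how often a wrong decision would follow. The differences in reaching level 3 apply only if the literal six-patient reading were actually used. No sample size changes.

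**What to change.** Reconcile the two *until* statements with the sentence on 2 or more DLTs, Figure 2, and Sections 4.2, 7.5 and 9.1. Keep one statement and delete the other. Set out separately the condition under which escalation proceeds and the condition under which it ends, so that the two do not overlap and every result for 3 and for 6 patients falls under exactly one of them. Settle whether the last clause refers to a stopping criterion having been met or to none having been met. Use one description of the design, adapted or traditional, and if adapted say what the adaptation is. Carry the same wording into the DSMB charter. Which clinical rule applies is for the sponsor and the DSMB to settle; the point is that the passages must agree.

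The cost is a wording correction in the protocol and an aligned charter, with no added patients, visits or procedures.

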4.3.2 Definition of Dose-limiting Toxicity (DLT)

A DLT is defined as any grade \geq 3 AE according to the NCI-CTCAE v. 5.0 observed at any time from the first administration of ES2B-C001 (alone or adjuvanted) to the 8 weeks thereafter, which despite standard supportive care and in the opinion of the Investigator, is possibly, probably, or definitely related to adjuvanted or non-adjuvanted ES2B-C001, or other event as described below. Investigators evaluation of relatedness to trial treatment administration should take concomitant medication into account.

DLTs will include:

- 1. Any grade ≥ 3 adverse events except:
 - a. Grade ≥ 3 nausea, vomiting, or diarrhea lasting ≤ 72hours with optimal medical therapy Grade 3 fatigue or anorexia lasting < 7 days.
 - b. Fever that occurs within 48 hours of IMP administration and resolves to Grade 2 within 48 hours and is fully resolved within 7 days.
 - c. Non-clinically relevant isolated biochemical abnormalities (e.g., isolated increase in gamma-glutamyltransferase [GGT]).
 - d. Laboratory values out of normal range without related clinical symptoms, clinically transient isolated in nature.
 - e. Laboratory abnormality that is asymptomatic and deemed by the Investigator not to be clinically significant.
- 2. Grade 3 autoimmune reactions, except Grade 3 autoimmune thyroiditis or other endocrine abnormality that can be managed by endocrine therapy.
- 3. Intolerable or > grade 3 injection-site reactions according to FDA guidance 2007 (table 16 appendix 2).
- 4. Grade 2 decrease in left ventricular ejection fraction (LVEF).
- 5. Treatment delay of >14 days due to any related adverse event(s).

In any case, the reported toxicity should be discussed between the Investigators and both the DSMB and the Sponsor. All toxicities will be graded using NCI-CTCAE Version 5.0 based on investigator assessment.

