4.3 Dose escalation

A DSMB will be appointed to oversee the trial. The composition and responsibilities of the DSMB is described in a dedicated charter, which will include additional instructions for the dose escalation procedure.

The decision to escalate the dose to the next dosing cohort or initiate the expansion part will be taken by the sponsor based on the DSMB recommendations. For the decision of dose escalation, AEs collected during the DLT period will be assessed by the DSMB. Other available data beyond the DLT evaluation period for all patients in the trial will also be assessed before a decision on escalation to the next dose level can be taken. Dose escalation rules will be based on the number of patients with AEs, specifically DLTs (Section 4.3.2). The DSMB will base recommendations on an evaluation of accumulated safety data and may include other available data, including data on immunogenicity (antibody titers) in their review.

Patients who discontinue for reasons other than toxicity before having DLT evaluable safety data may be replaced at sponsor's discretion.

A schedule of trial procedures is provided in Section 1.3. The administration of adjuvanted and non-adjuvanted ES2B-C001 is described in Section 6 and the trial assessments are described in Section 8.

The dose escalation will include 3 planned dose level cohorts with adjuvanted ES2B-C001 (Section 6.2).

Enrollment will be fully staggered in each of the populations, meaning that an observation period of 3 weeks plus 24 hours is foreseen before the second patient is dosed in one cohort. Dosing of the next subject in each cohort should not take place until 1 week after the preceding patient has received the first dose. Prior to dosing the second patient, safety and reactogenicity data from the previous patient will be discussed at a pre-dosing call between PI(s), CRO medical monitor, and

Clinical Study: ES2B-C001-S01 EU CT No.: 2024-516333-12-00

Sponsor. At subsequent administrations, pre-dosing calls will be scheduled if safety concerns warrant it. This will ensure an evaluation of safety prior to administration of the next patients.

Any safety concerns, such as potential DLTs and/or events that may meet a criterion for initiation of rescue medication, will be escalated to the DSMB who will review accumulated safety data and may provide recommendations for trial adjustments e.g., applying additional overnight stays for patients.

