Grade 4	An AE that has life-threatening consequences; for which urgent intervention is indicated; that puts the subject at risk of death at the time of the event if immediate intervention is not undertaken; or that causes blindness or deafness.
Grade 5	The termination of life as a result of an AE.

Assessment of Causality

- The PI will assess the causality/relationship between the study drug and the AE based on medical judgment and considering the definitions of the "Assessment of Relationship of Adverse Events to Investigational Medicinal Product" described in Table 16, and all contributing factors. The investigator is obligated to assess the relationship between trial intervention and each occurrence of each AE/SAE.
- For causality assessment, the investigator will also consult the IB for ES2B-C001 and/or
 [adjuvant] . The investigator may change their opinion of causality in light of
 follow-up information and send an SAE follow-up report with the updated causality
 assessment.
- The causality assessment is one of the criteria used when determining regulatory reporting requirements.

Clinical Study: ES2B-C001-S01 EU CT No.: 2024-516333-12-00

Table 16: Assessment of relationship of Adverse Events (AEs) to investigational medicinal product (IMP).

	Assessment of Relationship of Adverse Events to IMP
Definitely Related	A clinical event, including laboratory test abnormality, occurs in a plausible time relationship to treatment administration, and which concurrent disease or other drugs or chemicals cannot explain. The response to withdrawal of the treatment (dechallenge*) should be clinically plausible. The event must be definitive pharmacologically or phenomenologically, using a satisfactory rechallenge† procedure if necessary.
Probably Related	A clinical event, including laboratory test abnormality, with a reasonable time sequence to administration of the treatment, unlikely to be attributed to concurrent disease or other drugs or chemicals, and which follows a clinically reasonable response on withdrawal (de-challenge). Rechallenge information is not required to fulfill this definition.
Possibly Related	A clinical event, including laboratory test abnormality, with a reasonable time sequence to administration of the treatment, but which could also be explained by concurrent disease or other drugs or chemicals. Information on treatment withdrawal may be lacking or unclear.

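### DLT exceptions 1a (nausea, vomiting, diarrhea) and 1b (fever) have no upper grade, so a short-lived related Grade 4 event of these types is not counted under item 1

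*Protocol*

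**What the plan says.** Protocol Section 4.3.2 opens with a general definition: an adverse event of Grade 3 or higher, within 8 weeks of the first dose, "which despite standard supportive care and in the opinion of the Investigator, is possibly, probably, or definitely related" to the vaccine. A numbered list follows. Item 1 repeats the Grade 3 or higher threshold and then lists exceptions. Two matter here:

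- **1a:** "Grade ≥ 3 nausea, vomiting, or diarrhea lasting ≤ 72hours with optimal medical therapy". The same exception goes on to cover fatigue and anorexia of less than 7 days, but only at Grade 3.
- **1b:** "Fever that occurs within 48 hours of IMP administration and resolves to Grade 2 within 48 hours and is fully resolved within 7 days".

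Table 15 (Section 12.3) describes Grade 4 as "An AE that has life-threatening consequences; for which urgent intervention is indicated".

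The DLT count is used in four places:

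- **Section 4.3.1, expansion and stop:** "If one of the 3 patients in a dosing cohort experiences a DLT, 3 additional patients are added to the same dose level cohort". Two or more DLT patients among the 6 stop escalation.
- **Section 4.3.1, the individual patient:** a patient with a DLT has dosing discontinued, subject to DSMB advice on restarting.
- **Section 7.5:** enrollment is halted temporarily at 2 or more of 6 in one dosing group.
- **Section 9.3.1:** the MTD is tied to a threshold of at least 33% of patients with a DLT.

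**The concern.** An exception for brief, manageable toxicity is normal in a DLT definition and is usually meant for Grade 3. Here the wording of 1a starts at Grade 3 and has no ceiling, and 1b is limited only by times of onset and resolution. An event that Table 15 calls life-threatening can meet either exception if it settles quickly enough.

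The drafting looks like an oversight. The other exceptions for clinical conditions are capped: fatigue and anorexia in 1a, and thyroiditis or other endocrine abnormality in item 2, are all limited to Grade 3. As written, Grade 4 fatigue lasting one day is not excepted, while Grade 4 vomiting lasting three days (72 hours) is. No reason is given for the difference.

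This is a first-in-human trial with 3 to 9 patients per dose level, so a single patient can decide whether a cohort is expanded or escalation stops. DLTs are also the first-listed primary endpoint (Section 3).

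**Working it through.** **Step 1. Does the wording of 1a and 1b reach Grade 4?**

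| Exception | Lower grade | Upper grade | Other limits |
|---|---|---|---|
| 1a, nausea, vomiting, diarrhea | 3 (stated) | none | at most 72 hours, optimal therapy |
| 1a, fatigue, anorexia | 3 (stated) | 3 (stated) | under 7 days |
| 1b, fever | 3 (from context) | none | onset within 48 hours, Grade 2 within 48 hours, resolved within 7 days |

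The lower grade in 1b follows from its place under a Grade 3 or higher rule and from the requirement that the fever fall to Grade 2. Only the ceiling is missing. Exceptions 1c to 1e state no grade either, but they concern laboratory findings without symptoms or clinical relevance and are not part of this point.

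**Step 2. Does anything else put such an event back in the count?**

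- The opening sentence of 4.3.2 does not, because item 1 qualifies it with the exceptions.
- Items 2 to 4 concern autoimmune reactions, injection-site reactions and LVEF.
- Item 5 does, but only if a related event delays treatment by more than 14 days. An event over within 72 hours, or within 7 days for fever, need not cause such a delay.
- Section 8.4.4 refers related SAEs to Section 7.5 for stopping rules. Section 7.5 has no SAE rule; its only numerical trigger is the DLT count.
- Section 10.7 has the DSMB check whether events reported as DLTs meet the criteria. Applied literally, those criteria exclude this event.

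**Step 3. What does one uncounted patient change?**

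Inputs: cohort sizes 3, 6 and 9 (Section 4.1) and the rules in Sections 4.3.1, 7.5 and 9.3.1. Formula: DLT patients / cohort size, before and after removing one patient.

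| If counted | As written | Consequence |
|---|---|---|
| 1/3 = 33.3% | 0/3 = 0% | 3 extra patients no longer required by the count |
| 2/6 = 33.3% | 1/6 = 16.7% | escalation stop, enrollment halt and 33% threshold all not triggered |
| 3/9 = 33.3% | 2/9 = 22.2% | 33% threshold not met |

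The patient concerned also falls outside the DLT discontinuation rule in 4.3.1. What remains is Section 7.1, under which unacceptable toxicity is a reason to consider stopping treatment.

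**Step 4. Planned size.** 3 dose levels × 3 = 9 and 3 × 9 = 27 reproduce the planned and maximum numbers in Section 9.1. Neither depends on the exceptions.

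**The case against.** The strongest reply is that the count is not the only control. Section 4.3.1 says "Dose escalation to a higher dose will be driven by an evaluation by the DSMB", and under Section 4.3 the DSMB assesses all adverse events from the DLT period. Section 4.3.2 requires reported toxicity to be discussed among investigators, DSMB and sponsor. A life-threatening event is an SAE (Section 12.2), reported within 24 hours (Section 8.4.1). The sponsor and investigators review the first patient's data before the second is dosed. The DSMB can add patients (Section 10.7), and its recommendation can stop the trial without reference to the count (Section 7.5). Discontinuation after a DLT is itself reversible on DSMB advice. All of this stands, and it limits the practical reach. A reader might infer that escalation could pass a related Grade 4 event unnoticed; the protocol does not support that. What the safeguards do not do is alter the definition, the reported DLT frequency or the numerical rules.

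A second reply is that the changes in the table would follow from removing any event from any DLT definition and do not measure how often this gap would matter. That is correct. They show sensitivity, not frequency. A reader might infer a sizeable rise in the chance of escalating, since the 3+3 rule yields a figure for any assumed event rate. The protocol gives no such rate. What it does report points to rarity: Section 2.1.3 describes only rare Grade 3 toxicity in more than 1,000 HER2-low patients given other HER2 vaccines, and Section 2.3.2 describes mainly mild to moderate systemic reactions with the adjuvant, fever among them.

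Third, grading follows CTCAE v5.0, whose term-specific grades are not reproduced. Whether each named term has a Grade 4, nausea for example, cannot be checked here. The point needs only one of vomiting, diarrhea or fever to have one.

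**Conclusion.** The point holds as a gap in the definition. A related Grade 4 nausea, vomiting, diarrhea or fever event that meets the time limits is not a DLT under item 1 and would be counted only through item 5. It therefore does not by itself trigger the 1/3 expansion, the 2/6 stop and enrollment halt, the 33% MTD threshold or the DLT discontinuation rule.

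The severity is minor to should-fix. The event is probably uncommon and the DSMB can act without the count, but the correction is small and this is a first-in-human trial. The conclusion assumes that the exceptions are applied as written and that at least one of vomiting, diarrhea and fever can be graded 4. No change in escalation probability is claimed.

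A reader might also take 1b to except fever with no starting grade. Context supplies Grade 3 as the floor, so that reading goes too far.

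**What to change.** Make two changes in Section 4.3.2:

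- **1a:** replace the opening grade (3 or higher) with Grade 3 for nausea, vomiting and diarrhea. Keep the 72-hour and optimal-therapy conditions.
- **1b:** begin with Grade 3 fever. Keep the onset and resolution times.

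It is tempting to add a sentence making Grade 4 events of these four types DLTs whatever their response to treatment. I would not. It would override the supportive-care qualifier in the opening definition for four terms only, so that a Grade 4 vomiting event responding to care would count automatically while another Grade 4 event responding to care might not. With the two changes above, these events fall under the same general definition as every other Grade 4 event.

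The cost is a protocol amendment with the approvals in Section 10.1, and matching text in the eCRF and the DSMB charter. Visits and the 27-patient maximum are unchanged, since expansion to 6 or 9 per cohort is already planned. The downside is an occasional additional DLT, which may expand a cohort or stop escalation earlier.
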